4. PATIENT SELECTION, ENROLLMENT, RESTRICTIONS, DISCONTINUATION AND WITHDRAWAL

Each patient must meet all of the inclusion criteria (**Section 4.1**) and none of the exclusion criteria (**Section 4.2**) for this study. Under no circumstances will there be exceptions to this rule.

4.1 Inclusion criteria

For inclusion in the study, patients should fulfill the following criteria:

1. Written informed consent and any locally-required authorization (e.g., HIPAA in the USA, EU Data Privacy Directive in the EU) obtained from the patient prior to performing any protocol-related procedures, including screening evaluations.
2. Age ≥ 18 years at time of study entry
3. Patients with diagnosis of HCC either by high-resolution imaging (triple-phase CT or MRI) and/or by tumor biopsy.
4. Patient is not on systemic treatment for diagnosis of HCC. Prior local therapy (eg.TACE, radioembolization, radiation) is allowed if treatment was more than 1 month prior to enrollment with evidence of viable HCC or recurrence. Patients who were on tyrosine-kinase inhibitors (sorafenib, regorafenib, lenvatinib) or other systemic treatments for HCC but considered non-responders or intolerant to treatment are allowed to participate.
5. HCC meeting Barcelona Clinic Liver Cancer (BCLC) stage B (intermediate stage), with measurable lesions on CT or MRI and without extrahepatic spread. Patients with BCLC stage A not considered candidates for transplant or surgery at the time of enrollment can participate if committed to remain on study for 6 months prior to consideration for alternative local therapies.
6. Disease that is technically amenable to DEB-TACE. Cases will be discussed with interventional radiology. At least 1 measurable lesion, that can be measured at baseline as ≥ 10 mm in the longest diameter (except lymph nodes, which must have a short axis ≥ 15 mm) with CT or MRI.
7. Eastern Cooperative Oncology Group (ECOG) performance status of 0 or 1
8. Body weight >30 kg
9. Child-Pugh Score of A or early B (score ≤ 8) without clinically significant ascites. Trace or small amounts of radiographic ascites without prior concern for malignant ascites or not associated with peritoneal carcinomatosis may be approved by the Protocol Chair.
10. Liver associated lab values:
 - AST ALT ≤ 5 x ULN (pre-treatment)
 - Total bilirubin: If cirrhosis present: Part of Child Pugh requirement.

If no cirrhosis present: total bilirubin \leq 2 mg/dL

11. Lab parameters to ensure adequate organ function (other than liver):

- Absolute neutrophil count of \geq 1,000/mm³
- Hemoglobin \geq 9.0g/dL
- Platelets \geq 75,000/mm³
- Albumin \geq 2.5 g/dL
- INR \leq 1.8 mg/dL
- Creatinine \leq 2.0 mg/dL or calculated creatinine clearance $>$ 50mL/minute or Measured creatinine clearance (CL) $>$ 40 mL/min or Calculated creatinine clearance CL $>$ 40 mL/min by the Cockcroft-Gault formula (Cockcroft and Gault 1976) or by 24-hour urine collection for determination of creatinine clearance:

Males:

$$\text{Creatinine CL (mL/min)} = \frac{\text{Weight (kg)} \times (140 - \text{Age})}{72 \times \text{serum creatinine (mg/dL)}}$$

Females:

$$\text{Creatinine CL (mL/min)} = \frac{\text{Weight (kg)} \times (140 - \text{Age})}{72 \times \text{serum creatinine (mg/dL)}} \times 0.85$$

12. Evidence of post-menopausal status or negative urinary or serum pregnancy test for female pre-menopausal patients. Women will be considered post-menopausal if they have been amenorrheic for 12 months without an alternative medical cause. The following age-specific requirements apply:

Women $<$ 50 years of age would be considered post-menopausal if they have been amenorrheic for 12 months or more following cessation of exogenous hormonal treatments and if they have luteinizing hormone and follicle-stimulating hormone levels in the post-menopausal range for the institution or underwent surgical sterilization (bilateral oophorectomy or hysterectomy).

Women \geq 50 years of age would be considered post-menopausal if they have been amenorrheic for 12 months or more following cessation of all exogenous hormonal treatments, had radiation-induced menopause with last menses $>$ 1 year ago, had chemotherapy-induced menopause with last menses $>$ 1 year ago, or underwent surgical sterilization (bilateral oophorectomy, bilateral salpingectomy or hysterectomy).

13. Patient is willing and able to comply with the protocol for the duration of the study including undergoing treatment and scheduled visits and examinations including follow up.

14. Patient who is willing to get tumor biopsies per the study schedule.

4.2 Exclusion criteria

Patients should not enter the study if any of the following exclusion criteria are fulfilled:

1. Involvement in the planning and/or conduct of the study (applies to both AstraZeneca staff and/or staff at the study site).

2. Participation in another clinical study with last dose of an investigational product \leq 30 days prior to start of study treatment.
3. Any concurrent anticancer therapy (chemotherapy, immunotherapy, endocrine therapy, targeted therapy, biologic therapy, tumour embolization, monoclonal antibodies) or receipt of the last dose \leq 30 days prior to start of study treatment (TACE). Concurrent use of hormonal therapy for non-cancer-related conditions (e.g., hormone replacement therapy) is acceptable.
4. Patients with vascular invasion or extrahepatic tumor.
5. Main portal vein tumor-related thrombosis present on imaging. Non-tumor related thrombosis is allowed.
6. Uncontrolled hepatic encephalopathy at time of enrollement.
7. Ascites that require ongoing paracentesis, within 4 weeks prior to the first scheduled dose, to control symptoms.
8. Any contraindications for embolization, including hepatofugal blood flow or portosystemic shunt.
9. Patients with detectable HBV viral load without active anti-viral treatment.
 - Patients with positive HepB surface antigen (HBsAg) and/or HepB core antibodies (anti-HBc) with detectable HBV DNA (\geq 10 IU/mL or above the limit of detection per local lab standard) are permitted on study if they are being treated with antiviral therapy with evidence of HBV stabilization or signs of viral response prior to enrollment. Patients who test positive for anti-HBc with undetectable HBV DNA ($<$ 10 IU/ml or under the limit of detection per local lab standard) do not require anti-viral therapy prior to enrollment. (See Section 7.2.1 for additional on-study testing and anti-viral requirements)
10. Any prior or concurrent malignancy or myeloproliferative disorder whose natural history or treatment has the potential to interfere with safety or efficacy assessment of this study's investigational drug
11. History of leptomeningeal carcinomatosis.
12. History of active primary immunodeficiency.
13. Active infection including tuberculosis (clinical evaluation that includes clinical history, physical examination and radiographic findings, and TB testing in line with local practice), or human immunodeficiency virus (positive HIV 1/2 antibodies).
14. Any unresolved toxicity National Cancer Institute (NCI) Common Terminology Criteria for Adverse Event (CTCAE) Grade \geq 2 from previous anticancer therapy with the exception of alopecia, vitiligo, and the laboratory values defined in the inclusion criteria:
 - Patients with Grade \geq 2 neuropathy will be evaluated on a case-by-case basis after consultation with the Study Physician.

- Patients with irreversible toxicity not reasonably expected to be exacerbated by treatment with durvalumab or tremelimumab may be included only after consultation with the Study Physician.

15. Active or prior documented GI bleeding due to ulcer or esophageal varices bleeding within 6 months Note: For patients with history of esophageal variceal bleeding or assessed as high risk for esophageal variceal by the treating investigator, adequate endoscopic therapy according to institutional standards is required for assessment of esophageal varices. History of bleeding from other causes adequately treated are allowed.

16. Major surgical procedure (as defined by the Investigator) within 28 days prior to the first dose of IP. Note: Local surgery of isolated lesions for palliative intent is acceptable.

17. Current or prior use of immunosuppressive medication within 14 days before the first dose of durvalumab or tremelimumab. The following are exceptions to this criterion:

- Intranasal, inhaled, topical steroids, or local steroid injections (e.g., intra articular injection)
- Systemic corticosteroids at physiologic doses not to exceed 10 mg/day of prednisone or its equivalent
- Steroids as premedication for hypersensitivity reactions (e.g., CT scan premedication)

18. Active or prior documented autoimmune or inflammatory disorders (including inflammatory bowel disease [e.g., colitis or Crohn's disease], diverticulitis [with the exception of diverticulosis], systemic lupus erythematosus, Sarcoidosis syndrome, or Wegener syndrome [granulomatosis with polyangiitis, Graves' disease, rheumatoid arthritis, hypophysitis, uveitis, etc]).

19. Patients with hypothyroidism (e.g., following Hashimoto syndrome) who are not stable on hormone replacement.

20. Any chronic skin condition that require systemic therapy.

21. History of allogenic organ transplantation.

22. History of pericarditis, cardiomyopathy or current use of defibrillator.

23. Patients with celiac disease not controlled by diet alone.

24. Uncontrolled intercurrent illness, including but not limited to, ongoing or active infection, symptomatic congestive heart failure, uncontrolled hypertension, unstable angina pectoris, cardiac arrhythmia, interstitial lung disease, serious chronic gastrointestinal conditions associated with diarrhea, or psychiatric illness/social situations that would limit compliance with study requirement, substantially increase risk of incurring AEs or compromise the ability of the patient to give written informed consent.

25. Receipt of live attenuated vaccine within 30 days prior to the first dose of IP. Note: Patients, if enrolled, should not receive live vaccine whilst receiving IP and up to 30 days after the last dose of IP.
26. Female patients who are pregnant or breastfeeding or male or female patients of reproductive potential who are not willing to employ effective birth control from screening to 90 days after the last dose of durvalumab monotherapy or 180 days after the last dose of durvalumab + tremelimumab combination therapy.
27. Known allergy or hypersensitivity to any of the study drugs or any of the study drug excipients.
28. Prior randomisation or treatment in a previous durvalumab and/or tremelimumab clinical study regardless of treatment arm assignment.
29. Patients who have received prior anti-PD-1, anti-PD-L1 or anti-CTLA-4 including durvalumab and tremelimumab.
30. Judgment by the investigator that the patient is unsuitable to participate in the study and the patient is unlikely to comply with study procedures, restrictions and requirements.
31. Procedures for withdrawal of incorrectly enrolled patients are presented in **Section 4.3**.

4.3 Withdrawal of patients from study treatment and/or study

Permanent discontinuation of Durvalumab and Tremelimumab

An individual patient will not receive any further investigational product if any of the following occur in the patient in question:

- An individual patient will not receive any further durvalumab + tremelimumab combination therapy or if their weight falls to 30kg or less
- An individual patient will not receive any further tremelimumab monotherapy if their weight falls to 35kg or less
- Withdrawal of consent
- Adverse event that, in the opinion of the investigator or the sponsor, contraindicates further dosing
- Patient is determined to have met one or more of the exclusion criteria for study participation at study entry and continuing investigational therapy might constitute a safety risk
- Pregnancy or intent to become pregnant
- Any AE that meets criteria for discontinuation as defined in **Appendix 1**.
- Unacceptable toxicity (See **Section 6.5** for definition)
- Grade ≥ 3 infusion reaction
- Patient noncompliance that, in the opinion of the investigator or sponsor, warrants withdrawal; e.g., refusal to adhere to scheduled visits
- Initiation of alternative anticancer therapy including another investigational agent
- Confirmation of PD and investigator determination that the patient is no longer benefiting from treatment with durvalumab + tremelimumab. Patients who are permanently

discontinued from further receipt of investigational product, regardless of the reason (withdrawal of consent, due to an AE, other), will be identified as having permanently discontinued treatment

- Patients who are permanently discontinued from receiving investigational product will be followed for safety per Section 10 and Study Schedule in Section 8, including the collection of any protocol-specified blood specimens, unless consent is withdrawn or the patient is lost to follow-up or enrolled in another clinical study. All patients will be followed for survival and information about subsequent cancer therapies. Patients who discontinue treatment without confirmed disease progression will continue to receive standard of care scans. Patients who decline to return to the site for evaluations will be offered follow-up by phone every 3 months as an alternative.

Withdrawal of consent

Patients are free to withdraw from the study at any time (IP and assessments) without prejudice to further treatment.

Patients who withdraw consent for further participation in the study will not receive any further IP or further study observation, with the exception of follow-up for survival, which will continue until the end of the study unless the patient has expressly withdrawn their consent to survival follow-up. Note that the patient may be offered additional tests or tapering of treatment to withdraw safely.

A patient who withdraws consent will always be asked about the reason(s) for withdrawal and the presence of any AE. The Investigator will follow up AEs outside of the clinical study.

If a patient withdraws consent, they will be specifically asked if they are withdrawing consent to:

- all further participation in the study including any further follow up (e.g., survival contact telephone calls)
- withdrawal of consent to the use of their study generated data
- withdrawal to the use of any samples

4.4 Replacement of patients

If a patient is lost to follow up after the first DEB-TACE or deemed not appropriate for further treatment with durvalumab or tremelimumab due to medical complications, patients will be replaced. If patients do not have treatment scans for reasons other than death, patients will be replaced.

[figure not shown]
[figure not shown]
[figure not shown]
5. INVESTIGATIONAL PRODUCT(S)

Tremelimumab

[figure not shown]
[figure not shown]
5.2 Dose and treatment regimens

[figure not shown]
[figure not shown]
5.2.1 Treatment regimens

All patients in this study will receive durvalumab and tremelimumab 2 weeks after initial DEB-TACE treatment. Patients will subsequently continue with their combination immunotherapy, while receiving DEB-TACE Q8W. Patients will only receive repeat DEB-TACE if there is residual tumor that can be targeted.

[figure not shown]
[figure not shown]

5.2.3 Study drug preparation of durvalumab and tremelimumab

5.2.4 Monitoring of dose administration

5.3 Specific procedure for DEB-TACE (Drug-eluting Bead Trans-arterial chemoembolization)

For this study, patients will continue to receive DEB-TACE as standard of care. Patients undergoing trans-arterial chemoembolization are pre-medicated with analgesics, antibiotics and anti-emetics per clinical standards.

6. TREATMENT PLAN

6.1 Patient enrolment

6.1.1 Procedures for handling patients incorrectly enrolled

Patients who are incorrectly enrolled and do not meet the eligibility criteria, but are not yet initiated on treatment should be withdrawn from the study. The treating physician will determine subsequent treatment plans.

6.2 Dosage and administration

6.3 Definition of Unacceptable Toxicity

The combination of tremelimumab and durvalumab has been previously tested in a dose-escalation study performed by AstraZeneca employing dose ranges of 1-10mg/kg q4weeks (tremelimumab) and 10-20mg/kg q2-4weeks (durvalumab). Patients treated in the 20 mg/kg durvalumab + 1 mg/kg tremelimumab group had the fewest AEs, Grade ≥ 3 AEs, SAEs, and treatment discontinuations due to AEs, but still showed strong evidence of clinical activity. This cohort had a lower number of treatment-related Grade ≥ 3 AEs or treatment related SAEs. No dose-limiting toxicities were reported. This is the dose level we will be administering for this study. Also, PK analysis indicated only minor impact of body weight (WT) on PK of both agents so to minimize errors and for ease of use the company have moved to a fixed-dose schedule of 1500 mg Q4W durvalumab (equivalent to 20 mg/kg Q4W) and 75 mg Q4W tremelimumab (equivalent to 1mg/kg Q4W).

Unacceptable toxicities will be evaluated from the time of first administration of durvalumab or tremelimumab until the Week 6 evaluation (prior to the second dose of durvalumab). Patients who do not remain on the study through the completion of this safety run-in period for reasons other than DLT will be replaced with another patient (see **Section 11.2.4** for details of safety run-in). Grading of unacceptable toxicities will follow the guidelines provided in the Common Terminology Criteria for Adverse Events (CTCAE) version 5.0.

An unacceptable toxicity will be defined as any toxicity occurring during the study that meets the criteria below. Toxicity that is clearly and directly related to the primary disease or to another etiology is excluded from this definition. The following will be unacceptable toxicities:

- Any Grade 4 irAE
- Any \geq Grade 3 colitis
- Any Grade 3 or 4 non-infectious pneumonitis irrespective of duration
- Any Grade 2 pneumonitis that does not resolve to \leq Grade 1 within 3 days of the initiation of maximal supportive care
- Any Grade 3 irAE, excluding colitis or pneumonitis, that does not downgrade to Grade 2 within 3 days after onset of the event despite optimal medical management including systemic corticosteroids or does not downgrade to \leq Grade 1 or baseline within 14 days
- Liver transaminase elevation $> 8 \times$ ULN or total bilirubin $> 5 \times$ ULN (other than the 1st week following DEB-TACE)
- Any Grade ≥ 3 asymptomatic amylase or lipase levels, hold study drug/study regimen, and if complete work up shows no evidence of pancreatitis, study drug/study regimen may be continued or resumed.

- Any grade \geq 2 myocarditis
- Any \geq Grade 3 non-irAE, except for the exclusions listed below

[figure not shown]
The definition excludes the following conditions:

[figure not shown]
- Grade 3 fatigue lasting \leq 7 days
- Grade 3 dermatologic AEs that are considered mild in severity but only considered grade 3 because of $>30\%$ body surface involvement
- Diarrhea, nausea, or vomiting that resolves to $<$ grade 3 within 24 hours of intervention
- Grade 3-4 hyperglycemia
- Grade 3 endocrine disorder (thyroid, pituitary, and/or adrenal insufficiency) that is managed with or without systemic corticosteroid therapy and/or hormone replacement therapy and the patient is asymptomatic
- Grade 3 inflammatory reaction attributed to a local antitumor response (e.g., inflammatory reaction at sites of metastatic disease, lymph nodes, etc)
- Grade 3 infusion-related reaction (first occurrence and in the absence of steroid prophylaxis) that resolves within 6 hours with appropriate clinical management
- Grade 3 or 4 neutropenia that is not associated with fever or systemic infection that improves by at least 1 grade within 3 days. Grade 3 or Grade 4 febrile neutropenia will be an unacceptable toxicity regardless of duration or reversibility
- Grade 3 or 4 lymphopenia
- Grade 3 thrombocytopenia that is not associated with clinically significant bleeding that requires medical intervention, and improves by at least 1 grade within 3 days
- Isolated Grade 3 electrolyte abnormalities that are not associated with clinical signs or symptoms and are reversed with appropriate maximal medical intervention within 3 days. Isolated Grade 3 amylase or lipase abnormalities that are not associated with clinical signs/symptoms or findings on imaging consistent with pancreatitis

Immune-related AEs are defined as AEs of an immune nature (i.e., inflammatory) in the absence of a clear alternative etiology. In the absence of a clinically significant abnormality, repeat laboratory testing will be conducted to confirm significant laboratory findings prior to designation as an unacceptable toxicity.

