This is an open-label, single institution study of combination treatment of tremelimumab and durvalumab with trans-arterial chemoembolization with drug-eluting microsphere beads (DEB-TACE) in patients with intermediate stage HCC. The purpose of this study is to determine the safety and efficacy of durvalumab and tremelimumab in this population who are receiving DEB-TACE as standard of care. Patients who have intermediate stage HCC according to Barcelona Clinic Liver Cancer (BCLC) criteria, who are eligible for locoregional treatment with DEB-TACE will be enrolled. 20 HCC patients will undergo DEB-TACE, followed by durvalumab 1500mg q4weeks and tremelimumab 300mg once within 2 weeks. Patients will continue with durvalumab q4weeks until progression of disease or the end of study or maximum 13 cycles. Patients will have radiographic surveillance every 6-8 weeks from their last DEB-TACE, and if there is residual tumor that can be targeted, patients will receive repeat DEB-TACE.

All patients will have pre- and post-TACE biopsies during the first DEB-TACE treatment and post-immunotherapy infusion biopsy.

Patients who are clinically stable at an initial confirmed progression may continue to receive study treatment, after the first overall time point assessment of PD until PD is confirmed on a follow-up scan (confirmed PD) if they do not show any significant toxicities. Patients will get a confirmatory scan, following the assessment of PD, at the next scheduled visit. Patients that continue on study after an initial PD will continue to receive durvalumab and tremelimumab at the same dose and schedule as they were treated with initially.

In addition, we will have 20 patient data for patients with HCC from our institutional database as exact matched control based on age, gender, tumor stage and Child-pugh score. We will evaluate the objective response rate (ORR) in comparison to the study group, using McNemar paired-sample test.

Number of Centers: 1

Study Population: 20

Patients with intermediate stage HCC, defined by the Barcelona Clinic Liver Cancer (BCLC) stage B with compensated cirrhosis who would be eligible for liver-directed therapy (e.g. DEB-TACE) as standard treatment.

Inclusion Criteria:

- Patients with diagnosis of HCC either by high-resolution imaging (triple-phase CT or MRI) and/or by tumor biopsy.

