- Judgment by the investigator that the patient is unsuitable to participate in the study and the patient is unlikely to comply with study procedures, restrictions and requirements.

Investigational Product(s), Dose, and Mode of Administration:

Durvalumab 1500mg Q4W plus tremelimumab 300mg once via IV infusion, starting at 2 weeks after first DEB-TACE procedure. This will be followed by durvalumab monotherapy 1500 mg via IV infusion Q4W, until progression or unacceptable toxicity (maximum 13 doses/cycles).

Study Assessments and Criteria for Evaluation:

Safety Assessments:

To ensure that the combination is safe, the first six patients will be treated and observed for toxicity for 1 cycle before continuation with further accrual. If ≤ 1 limiting toxicity events occur in the first 6 patients, we will proceed with additional accrual to complete a total of 20 patients for the safety evaluation. If > 1 limiting toxicity events occur among the first 6 patients, then three additional patients will be enrolled (i.e. a total of 9 patients). If ≤ 2 limiting toxicity events occur in the 9 patients, we will proceed with additional accrual to complete a total of 20 patients for the safety assessment. If > 2 limiting toxicity events occur, we will pause the enrollment pending safety review.

Efficacy Assessments:

The primary endpoint is objective response using modified RECIST (mRECIST) criteria. The regimen would be considered of insufficient activity for further study if the response rate is 30%

or less, and the minimum required level of efficacy that would warrant further study with the proposed regimen is a 60% response rate.

Statistical Methods and Data Analysis:

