3. STUDY DESIGN

This is an open-label, single institution, single arm study of combination treatment of durvalumab and tremelimumab in patients with intermediate stage HCC (BCLC B) undergoing trans-arterial chemoembolization.

Patients will be recruited from the Johns Hopkins Multidisciplinary Liver Cancer Clinic, general liver clinic, inpatient admissions with newly diagnosed HCC, and direct referrals to Interventional Radiology for DEB-TACE treatment. Once their diagnosis and staging is confirmed in Liver radiology tumor board as intermediate stage, patients will be screened for enrollment.

Enrolled patients will proceed with DEB-TACE procedure along with pre-treatment biopsy of tumor and surrounding non-tumor tissue. Following their DEB-TACE procedure, patients will be followed in 7-10 days in hepatology clinic with labs for any new decompensating signs or symptoms. If the patient does not have any ongoing new decompensation, they will proceed with a 2nd biopsy, followed by 1st infusion of durvalumab 1500mg and tremelimumab 300mg 2 weeks after DEB-TACE. This will be followed by durvalumab 1500mg q4weeks until progression of disease, the end of study, or maximum 13 cycles.

All patients will receive repeat DEB-TACE every 8 weeks if there is residual tumor that can be targeted. A third biopsy will be done after 2 doses of durvalumab infusion during their second DEB-TACE procedure at week 8, unless the patient has CR.

Patients will have an MRI (or CT if contraindicated) at Week 6 and Week 14, then every 3 months unless additional DEB-TACE is needed. Patients who are clinically stable at initial disease progression may continue to receive study treatment until PD is confirmed on a follow-up scan (confirmed PD) if they do not show any significant toxicities. Patients will get a confirmatory scan, following the assessment of PD, at the next scheduled visit. Patients will continue to receive durvalumab and tremelimumab with the same dose and schedule as they were treated with initially.

Additionally, 20 patients from the institutional database will be selected as exact matched control based on age, gender, tumor stage and Child-Pugh score. We will evaluate the objective response rate (ORR) in comparison to the study group, using McNamer paired-sample test.

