8.2.3 MRI or CT

Patients will be recommended to have an MRI at week 6 following their first DEB-TACE date. If MRI is contraindicated for any medical reasons (e.g. history of metals in the body, severe claustrophobia), patients may have a CT scan (liver-dedicated CT). Tumor response will be assessed according to the modified RECIST criteria (mRECIST). mRECIST takes into account reduction in viable tumor using contrast-enhanced radiologic imaging rather than strict tumor size. Details of response measurement are under Section 9. If there is complete response at the 1st surveillance imaging, patients will continue with their monthly infusion with durvalumab and tremelimumab for total of 4 cycles, with repeat MRI as scheduled at week 14. If there's ongoing CR, they will have MRI monitoring every 3 months. For all other response after the 1st MRI, patients will get repeat DEB-TACE, along with scheduled immunotherapy treatment and scans per the study schedule.

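### Section 6.3 presents the safety record of tremelimumab 1 mg/kg (75 mg Q4W) as that of this study's dose, but the study gives 300 mg once; multi-dose wording also remains in several other sections

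*Combined protocol and SAP*

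**What the plan says.** The regimen is stated consistently where the design is set out. The synopsis, under investigational product and dose, gives "Durvalumab 1500mg Q4W plus tremelimumab 300mg once via IV infusion, starting at 2 weeks after first DEB-TACE procedure". The synopsis design paragraph agrees: "followed by durvalumab 1500mg q4weeks and tremelimumab 300mg once within 2 weeks". Section 3 gives tremelimumab 300 mg at the first infusion only, then continues: "This will be followed by durvalumab 1500mg q4weeks until progression of disease, the end of study, or maximum 13 cycles". Section 1.3.5.1 names 300 mg for one dose as the regimen under study. Figure 2 carries one tremelimumab mark, at Week 2, without a milligram amount.

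Section 6.3 says otherwise. It describes an earlier dose-escalation study and reports: "Patients treated in the 20 mg/kg durvalumab + 1 mg/kg tremelimumab group had the fewest AEs". It notes that no dose-limiting toxicities were reported, and then says: "This is the dose level we will be administering for this study". The following sentence converts that pair to fixed doses of durvalumab 1500 mg and tremelimumab 75 mg, both every 4 weeks.

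Section 8.2.3 deals with a patient who has a complete response at the first scan: "patients will continue with their monthly infusion with durvalumab and tremelimumab for total of 4 cycles". Other places also describe repeated tremelimumab:

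- Section 1.3.5.2 has four combination doses, then up to eight of durvalumab.
- Section 1.3.5.3 lists both 300 mg once and 75 mg every 4 weeks as part of this study.
- Section 5.2.1 has patients continue combination immunotherapy.
- Section 9.1 sets a restart condition based on completing four combination doses.
- The post-progression sentences in the synopsis and Section 3 keep both drugs going on the initial dose and schedule.

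**The concern.** Section 6.3 leads into the definitions that the safety run-in uses. A reader who starts there, such as an ethics committee member or a new co-investigator, will conclude that this study's tremelimumab dose is the one with the mildest record in the dose-escalation study. The error is therefore in the reassuring direction. It also conflicts with Section 1.3.5.1, which discloses the higher peak concentration and the absence of clinical data. Section 1.4.2.3 shows how it should be done: it quotes adverse-event rates for the same cohort and labels them with that cohort's dose.

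The remaining multi-dose wording matters for a different reason. Some of it is phrased as an instruction, so the protocol contains two answers to the question of how many tremelimumab infusions a patient receives.

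**Working it through.** **Inputs.** Reference weight 75 kg (1.3.5.3). Fixed doses in 6.3: durvalumab 1500 mg and tremelimumab 75 mg. Study dose: tremelimumab 300 mg once (synopsis, 1.3.5.1, 3). Predicted Cmax (1.3.5.1): 78 µg/mL after 4 mg/kg once, 19 µg/mL after the first 1 mg/kg dose, 25 µg/mL after the fourth.

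**1. The plan's own conversion.** Dose per kg = fixed dose / weight.
- Durvalumab: 1500 / 75 = 20 mg/kg.
- Tremelimumab: 75 / 75 = 1 mg/kg.

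Both reproduce what 6.3 states.

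**2. The dose actually planned.**
- Tremelimumab: 300 / 75 = 4 mg/kg, not 1 mg/kg.
- Against the fixed 75 mg dose: 300 / 75 mg = 4-fold per infusion, at any body weight.

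So the durvalumab half of the statement in 6.3 fits this study and the tremelimumab half does not. The sentence cannot be read as meaning durvalumab alone, because the next one converts both drugs.

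**3. Peak and total exposure.**
- Cmax: 78 / 19 = 4.1-fold over the first 1 mg/kg dose; 78 / 25 = 3.1-fold over the fourth.
- Total dose: 4 × 75 mg = 300 mg, equal to 1 × 300 mg. This agrees with the statement in 1.3.5.1 that overall exposure is similar.

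**4. Dose counts.**
- Figure 2, durvalumab: Weeks 2, 6, 10 and 14, plus nine visits from Week 18 to Week 50, gives 13, matching the maximum of 13.
- Figure 2, tremelimumab: 1.
- Section 1.3.5.2: 4 + 8 = 12 durvalumab doses, not 13.
- Section 8.2.3 read literally: four combined cycles from Week 2 fall at Weeks 2, 6, 10 and 14. Less the one scheduled, that leaves 3 unscheduled tremelimumab infusions, or 2 if the Week 6 infusion is given before the scan result is known. No milligram amount is stated. A limit of four cycles would also conflict with up to 13 of durvalumab.

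**5. Does the design depend on this?** The Simon rule (stop if 2 or fewer of 8 respond; promising if 9 or more of 20 respond) uses only counts and assumed response rates.
- Early stop = P(X₁ ≤ 2 | 8, p).
- Promising = Σ over x = 3 to 8 of P(X₁ = x | 8, p) × P(X₂ ≥ 9 − x | 12, p).
- At p = 0.30: early stop 0.552, type I error 0.0999. At p = 0.60: power 0.912.

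These agree with the stated 0.55, 0.1 and 90%, and no dose enters the formulas. The run-in rule is likewise a count of toxicity events in 6 or 9 patients.

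**The case against.** The best defence is that the regimen is not in doubt. The synopsis, Sections 1.3.5.1 and 3 and Figure 2 agree, and 1.3.5.1 is frank about the missing clinical data. On this view the rest is text carried over from a multi-dose regimen. It is also fair to say that 4 mg/kg at 75 kg lies inside the 1 to 10 mg/kg range tested in the earlier study. All of that stands, but none of it makes the 1 mg/kg cohort's record the record of a dose four times as large, and Section 6.3 makes a statement specific to this study.

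On Section 8.2.3 the defence is stronger. A reader might infer that early complete responders are to receive two or three extra tremelimumab infusions. The documents do not support that as the plan's intent. Footnote a to Figure 2 addresses these same patients: they stop DEB-TACE and otherwise stay on the study regimen, which has one tremelimumab dose. The phrase sits in an imaging section, gives no amount, and resembles the loose pairing of the two drugs elsewhere. The wording still needs correcting, but as leftover text and not as a hidden dosing arm.

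Nor does it add much that such infusions would fall after the run-in window, which runs "until the Week 6 evaluation (prior to the second dose of durvalumab"). Twelve of the 13 durvalumab doses fall after it too, and adverse events are recorded until 90 days after the last dose.

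Section 5.2.2 and the body of 6.2 are not in the public copy, so nothing can be said about the dosing or retreatment instructions there. Whatever they contain, 6.3 still contradicts the synopsis and Section 3.

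**Conclusion.** The point holds as an error of statement. Section 6.3 attributes to this study a tremelimumab dose, and with it a safety record, that belong to a regimen with one quarter of the dose per infusion. The documented difference is 4-fold per infusion and 3- to 4-fold in predicted Cmax, with similar total exposure. The mg/kg figure rests on the protocol's 75 kg reference weight; the comparison of 300 mg with 75 mg needs no weight assumption. The single tremelimumab mark in Figure 2 is read from a damaged table, but it agrees with the synopsis and Section 3.

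Two stronger conclusions are not supported. One is that patients were given the wrong dose or extra doses; the documents contain no dosing records. The other is that the run-in or the Simon design is compromised; their thresholds and operating characteristics do not depend on the dose text. The point should be corrected because it concerns the tremelimumab dose in the toxicity section and conflicting treatment wording elsewhere.

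**What to change.** **Section 6.3.** Delete the sentence "This is the dose level we will be administering for this study". Label both the cohort data and the 75 mg every-4-weeks schedule as coming from the earlier 1 mg/kg Q4W regimen. State that this study gives tremelimumab 300 mg once, about 4 mg/kg at 75 kg, and that the cohort does not cover that dose.

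**Section 8.2.3.** Remove tremelimumab and the four-cycle limit from the sentence on early complete responders. Say that durvalumab alone continues, up to 13 cycles in total, consistent with footnote a to Figure 2.

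**Alignment.** Bring 1.3.5.2 (including its heading and its total of 12), 1.3.5.3, 5.2.1, the restart condition in 9.1, and the post-progression sentences in the synopsis and Section 3 into line with one tremelimumab dose and up to 13 durvalumab doses. Check Sections 5.2.2 and 6.2 in the full protocol at the same time.

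**Cost.** One text amendment. It needs no new data or patients, and no threshold, sample size or analysis changes.
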